9.3 Analysis Sets

For the purposes of analysis, the following analysis sets are defined:

Participant Analysis Set	Description
Enrolled Set	The enrolled set will contain all participants who were enrolled to study treatment. A participant will be considered as enrolled if he has signed the informed consent form and is assigned to treatment.
Safety Set	The safety set will contain all participants who receive at least one dose of study intervention.
Full Analysis Set	The full analysis set analysis set will contain all participants who signed an informed consent form and received two administrations of study intervention and completed all visits for testosterone measurement (Day 29, Day 85, Day 141, Day 169, Day 253, Day 309 and Day 337). Note, a participant will be included in the full analysis set if their testosterone measurement is ≥ 50 ng/dL before the end of treatment, end of study or withdrawn from study, whichever is earlier.
Per Protocol Set	The per protocol set will contain all participants from the full analysis set who did not experience any major protocol deviations that may interfere with efficacy evaluation.

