4 ANALYSIS SETS

Screened Set

The screened set will contain all participants who signed an informed consent for this study. In case of re-screening, the participant will be counted once only in the screened set. The previous site and assigned subject numbers will be collected to link the first and second screening data.

Enrolled Set

The enrolled set will contain all participants who were enrolled to study treatment. A participant will be considered as enrolled if he has signed the informed consent form and is assigned to treatment.

Intent-to-Treat Set

The intent-to-treat (ITT) Set will contain all participants who signed an informed consent form and received at least one administration of study intervention and have a serum testosterone level <1.735 nmol/L (50 ng/dL) on Day 1 (pre-dose measurement).

Full Analysis Set

The full analysis set (FAS) will contain all participants who signed an informed consent form and received two administrations of study intervention and completed all visits for testosterone measurement (Day 29, Day 85, Day 141, Day 169, Day 253, Day 309 and Day 337). Note, a participant will be included in the FAS if his testosterone measurement is ≥ 50 ng/dl before the end of treatment, end of study or withdrawn from study, whichever is earlier.

Per Protocol Set

The per protocol (PP) set will contain all participants from the FAS who did not experience any major protocol deviations that may interfere with efficacy evaluation (refer to section 5.3 for details regarding the management of deviations).

Safety Set

The safety set will contain all participants who receive at least one dose of study intervention.

Associated Procedure / Instruction Reference	319480-SOP
Form Reference	080091-FOR v7.0

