5.7.2 Analysis of Primary Efficacy Endpoint

5.7.2.1 Primary Efficacy Endpoint, Treatment Effect and Estimand Definition

To assess the primary objective, the primary estimand will be defined by the following attributes:

- Population: participants with locally advanced and/or metastatic prostate cancer previously treated and castrated with a GnRH analogue as defined by the listed Inclusion/Exclusion criteria in sections 5.1 and 5.2 of the protocol, respectively.
- Variable/Endpoint: castration maintenance rate during the study defined as percentage of participants castrated (testosterone < 1.735 nmol/L (50 ng/dL)) at Day 29, Day 85, Day 141, Day 169, Day 253, Day 309 and Day 337, with two complete study intervention administrations.
- Key Intercurrent event (ICE):
 - (a) ICE 1 - Subjects discontinued from study prior to Day 337 without evidence of inadequate testosterone suppression (testosterone measurement \geq 50 ng/dL)
The testosterone values of these participants will not be considered for the main analysis (principal stratum strategy).
 - (b) ICE 2 - Subjects with at least one planned testosterone measurement missing on or prior to Day 337 without evidence of inadequate testosterone suppression (testosterone measurement \geq 50 ng/dL)
The testosterone values of these participants will not be considered for the main analysis (principal stratum strategy).

Associated Procedure / Instruction Reference	319480-SOP
Form Reference	080091-FOR v7.0

(c) ICE 3 - Subjects discontinued treatment prior to receiving the second study intervention administration without evidence of inadequate testosterone suppression (testosterone measurement ≥ 50 ng/dL)
The testosterone values of these participants will not be considered for the main analysis (principal stratum strategy).

(d) ICE 4 - Subjects received a prohibited medication during the study
Prohibited medication with impacts on the testosterone value will be identified through blinded data review. Subjects receiving identified prohibited medication (for example, finasteride, dustasteride, or abiraterone) will be included in the primary analysis as non-responder. In contrast, all testosterone measurements from subjects receiving prohibited medications other than identified ones during the study will be included in the primary analysis (composite strategy).

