5.7.3 Analysis of Key Secondary Efficacy Endpoints

5.7.3.1 Secondary Efficacy Endpoints

The secondary efficacy endpoints are listed below:

- Percentage of participants castrated at each timepoint on Day 29, Day 85, Day 141, Day 169, Day 253, Day 309 and Day 337 (castration defined as testosterone <1.735 nmol/L (50 ng/dL))
- Percentage of participants with a serum testosterone level <0.694 nmol/L (20 ng/dL) during the study
- Percentage of participants with a serum testosterone level <0.69 nmol/L (20 ng/dL) at each timepoint on Day 29, Day 85, Day 141, Day 169, Day 253, Day 309 and Day 337
- Percentage of participants castrated on Day 3 and Day 7 after each injection administered on Day 1 and Day 169 (castration defined as testosterone <1.735 nmol/L (50 ng/dL))
- Percent change in PSA from baseline (prior to injection) at Day 169 and Day 337 (Percent change in PSA defined as the absolute value of difference between the PSA values at Day 169 and Day 337 and the baseline value divided by the baseline value).

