5.7.3.2 Main Secondary Analysis

The same strategies as those for the primary estimand will be used for the main secondary analysis in the FAS, with castration maintenance criteria being replaced with 0.694 nmol/L (20 ng/dL) whenever applicable.

For binary secondary endpoints, including castration maintenance (<50 ng/dL) rate at specific timepoints, castration maintenance (<20 ng/dL) rate during the study, castration maintenance (<20 ng/dL) rate at each timepoint, castration maintenance rate along with the associated 95% exact CI will be provided. For percent change in PSA from baseline at Day 169 and Day 337, descriptive statistics will be provided.

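### In the <20 ng/dL during-study analysis, incomplete men stay in the FAS only at 50 ng/dL or more, so those with an observed 20-49 ng/dL, already failures, are dropped

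*SAP*

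**What the plan says.** The endpoint is listed in SAP 5.7.3.1 as "Percentage of participants with a serum testosterone level <0.694 nmol/L (20 ng/dL) during the study". For the binary secondary endpoints, SAP 5.7.3.2 plans that the "castration maintenance rate along with the associated 95% exact CI will be provided". The same section carries over the strategies of the primary estimand, "in the FAS, with castration maintenance criteria being replaced with 0.694 nmol/L (20 ng/dL) whenever applicable".

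The FAS in SAP 4 requires that a man "received two administrations of study intervention and completed all visits for testosterone measurement" on the seven endpoint days. One exception is given for men who do not meet this: "a participant will be included in the FAS if his testosterone measurement is ≥ 50 ng/dl". Protocol 9.3 has the same exception: "a participant will be included in the full analysis set if their testosterone measurement is ≥ 50 ng/dL before the end of treatment". Neither document defines a version of the FAS with a 20 ng/dL exception.

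In SAP 5.7.2.1, ICE 1 to 3 cover men who leave the study, miss a planned testosterone sample, or stop before the second injection, in each case with no value of 50 ng/dL or more. For each the instruction is: "The testosterone values of these participants will not be considered for the main analysis (principal stratum strategy").

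SAP 5.7.3.4 adds one sensitivity analysis of this endpoint: a Kaplan-Meier estimate at Day 337 with the Primary-S3 strategies, which use the ITT set, and the criterion changed to <20 ng/dL.

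**The concern.** For the primary endpoint, the value that keeps an incomplete man in the FAS (50 ng/dL or more) is also the value that makes him a failure. Every incomplete man with an observed failure is therefore counted. Once the failure threshold moves to 20 ng/dL and the FAS exception stays at 50, that match is lost. A man with 30 ng/dL on Day 85 who leaves on Day 120 has failed the <20 endpoint whatever might have followed, yet he is in neither numerator nor denominator. A man with 55 ng/dL who leaves on the same day is counted as a failure. The SAP gives no reason for treating the two differently.

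At stake is the point estimate and exact interval for a named secondary objective. There is also an ambiguity for the programmer, since the SAP does not say how far the change of criterion reaches.

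**Working it through.** **The plan's own figures.** The documents state no figure for the <20 ng/dL endpoint. The primary design (SAP 2.3) supplies the numbers of men used below, and it reproduces. With n = 130 and a null rate of 90%, the smallest count with an exact binomial tail of at most 0.025 is 124 (type I error 0.0207). Power at 97% is 0.903, against the stated approximate 90%. Enrolment is 130/(1 - 0.10) = 144.4, rounded up to 145. None of this is in dispute.

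**The rules side by side.** I read the during-study <20 endpoint on the same seven days as the primary. Values of 20-49 mean at least 20 and below 50 ng/dL.

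| Man | Status on <20 endpoint | FAS as written | ICE 1-3 at 50 | ICE 1-3 at 20 |
|---|---|---|---|---|
| Complete | known | in | not triggered | not triggered |
| Incomplete, a value of 50 or more | failure | in | not triggered | not triggered |
| Incomplete, highest value 20-49 | failure | **out** | set aside | **not triggered** |
| Incomplete, all observed values below 20 | unknown | out | set aside | set aside |

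The third row is the problem. If the change of criterion reaches the ICE clause, the ICE rule keeps this man and the FAS removes him. If it reaches only the definition of response, the ICE rule and the FAS agree, and a known failure is dropped by both. Under either reading the FAS as worded leaves him out.

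**Size.** Assumptions: 145 men dosed, 130 complete, 145 - 130 = 15 incomplete with no value of 50 or more, and k of those 15 with an observed 20-49 ng/dL. Let x be the completers who stay below 20.

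- Rate in the FAS as written: x/130.
- Rate under the primary rule applied at 20 ng/dL: x/(130 + k).
- Difference: (x/130) × k/(130 + k).

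| x | FAS rate | k = 1 | k = 3 | k = 5 |
|---|---|---|---|---|
| 104 | 80.0% | 79.4% (-0.61) | 78.2% (-1.80) | 77.0% (-2.96) |
| 117 | 90.0% | 89.3% (-0.69) | 88.0% (-2.03) | 86.7% (-3.33) |
| 124 | 95.4% | 94.7% (-0.73) | 93.2% (-2.15) | 91.9% (-3.53) |

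That is about 0.6 to 0.7 points per man. For x = 117 the exact 95% interval moves from 83.5-94.6% to 81.2-93.0% with k = 3. The arithmetic limit, all 15 incomplete men at 20-49, is 117/145 = 80.7%. Neither k nor x comes from the documents. Under ICE 2 a single missing planned sample makes a man incomplete, so their number is not tied to the 10% drop-out figure.

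**Is the FAS rate biased against the true rate?** Suppose completers and incomplete men alike fail at 20%. Then 3 of the 15 incomplete men fail and 12 do not. The FAS gives 104/130 = 80.0%. All dosed men give (104 + 12)/145 = 116/145 = 80.0%. Adding only the 3 failures gives 104/133 = 78.2%. In this case the FAS rate is right and the primary-style rule is low.

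**The case against.** Four objections deserve weight.

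*There need be no contradiction.* A reader might infer that the SAP gives two instructions that cannot both be followed. That holds only if the change of criterion moves the ICE threshold and leaves the FAS note alone. Read narrowly, nothing but the response criterion moves, and ICE 1-3 keep their own threshold of 50. Read most broadly, 20 replaces 50 in the FAS note as well, and the problem disappears. The objection stands: this is an ambiguity. But the broad reading has to be supplied by the reader, since the FAS is defined in SAP 4 with a fixed 50, and the narrow reading still drops known failures.

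*Overstatement is not shown.* A reader might infer that the true <20 rate is overstated. The documents do not support that. The declared strategy is principal stratum, and incomplete men who stayed below 20 are set aside too. Upward bias would require values of 20-49 to be linked to incompleteness, and the withdrawal rule in Protocol 7.2 operates above 50 ng/dL. This stands in full. What remains is a comparison with the SAP's own rule for the primary endpoint.

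*The failures are counted elsewhere.* The Kaplan-Meier analysis in SAP 5.7.3.4 uses the ITT set and would count the man with 30 ng/dL on Day 85, because that value precedes his first missing sample. This largely stands. It can still lose a 20-49 value that follows the first missing one in a man with two or more missing values, if the evidence clause of Primary-S3 stays at 50. It also changes the analysis set, the missing-data handling and the summary measure together, so it neither corrects nor explains the main estimate.

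*Little depends on it.* The SAP plans no formal testing, and the 90% criterion applies to the primary endpoint only. This stands and sets the priority.

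**Conclusion.** The point holds as a threshold mismatch. On the literal text, the main <20 ng/dL during-study estimate drops incomplete men with an observed 20-49 ng/dL and keeps incomplete men at 50 or more as failures. It is therefore not built as the primary analysis is. Compared with the primary rule applied at 20 ng/dL, the reported rate is higher by about 0.6 to 0.7 points per such man, assuming 130 completers of whom 80% to 95% stay below 20. How many such men there will be is unknown, so no total can be given; with none, the estimate is unchanged.

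The finding does not extend to proven bias against the true rate or to an unavoidable contradiction in the SAP. It does not touch the primary endpoint, the sample size or any type I error. Low priority, but cheap to settle before the analysis.

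**What to change.** State in SAP 5.7.3.2 that, for the <20 ng/dL during-study endpoint, both the FAS retention exception and the evidence threshold in ICE 1-3 are an observed value of 20 ng/dL (0.694 nmol/L) or more that counts as a failure of that endpoint. Apply the same threshold to the evidence clause of Primary-S3 where SAP 5.7.3.4 uses it. Keep the current FAS for the <50 ng/dL endpoints.

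The cost is a short addition to each of the two sections and one extra population flag; no new data are needed. The <20 rate may come out slightly lower. It should be described as conservative, because incomplete men who stayed below 20 remain excluded, as the corresponding men are in the primary analysis.

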2.2 Background

Prostate cancer is the second most common cancer in the male population and thus the sixth cause of death from cancer in men over 50 in the western world [Sung 2021]. Prostate cancer is androgen dependent, with most patients initially responding to androgen deprivation therapy (ADT). However, after 1 to 2 years of treatment, advanced prostate cancer eventually progresses to castration resistant prostate cancer.

Androgen receptor signalling plays an important role in the development of prostate cancer. Gonadotropin-releasing hormone, also known as luteinizing hormone releasing hormone (LHRH) is released in a pulsatile manner by the hypothalamus and stimulates the pituitary to release in pulses the gonadotropins luteinizing hormone (LH) and follicle stimulating hormone (FSH). LH stimulates the production of testosterone by the testis; however, approximately 5% of circulating testosterone is independently produced by the adrenal glands. FSH plays a role in the regulation of spermatogenesis.

Since the pioneering studies of Huggins and Hodges [1941, 1941a] in the 1940's about the role played by the testicular androgen development and progression of prostate cancer cells, the mainstay of treatment for advanced prostate cancer has been androgen deprivation by bilateral orchiectomy and/or oestrogen therapy. The limitations of these therapeutic modalities led to the development of GnRH analogues, which have made pharmacological castration the preferred option among many patients with metastatic disease [Filicori 1994].

The therapeutic activity of the GnRH agonists is achieved via pituitary down-regulation of their own receptors achieved by continuous and chronic administration, providing almost complete suppression of LH and FSH secretion leading to suppression of testicular function.

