3 OBJECTIVES AND ENDPOINTS

Table 3 Objectives and Endpoints

Objectives	Endpoints
Primary	

 To evaluate the efficacy of triptorelin embonate 22.5 mg 6-month formulation administered subcutaneously in maintaining serum testosterone castrate levels in participants with advanced prostate cancer previously treated and castrated with a GnRH analogue 	
 Percentage of participants maintaining castrate levels of serum testosterone during the study (maintenance of castration defined as testosterone <1.735 nmol/L (50 ng/dL) at Day 29, Day 85, Day 141, Day 169, Day 253, Day 309 and Day 337)
Secondary	

 To evaluate the efficacy of triptorelin embonate 22.5 mg 6-month formulation administered subcutaneously on castration 	
 Percentage of participants castrated at each timepoint on Day 29, Day 85, Day 141, Day 169, Day 253, Day 309 and Day 337 (castration defined as testosterone <1.735 nmol/L (50 ng/dL))

 To evaluate the efficacy of triptorelin embonate 22.5 mg 6-month formulation administered subcutaneously on testosterone levels <0.694 nmol/L (20 ng/dL) 	
 Percentage of participants with a serum testosterone level <0.694 nmol/L (20 ng/dL) during the study Percentage of participants with a serum testosterone level <0.69 nmol/L (20 ng/dL) at each timepoint on Day 29, Day 85, Day 141, Day 169, Day 253, Day 309 and Day 337

 To demonstrate the effect of triptorelin embonate 22.5 mg 6-month formulation administered subcutaneously to suppress the 'acute-on-chronic' effect following the administration of the second dose 	
 Percentage of participants castrated on Day 3 and Day 7 after each injection administered on Day 1 and Day 169 (castration defined as testosterone <1.735 nmol/L (50 ng/dL))

 To demonstrate the effect of triptorelin embonate 22.5 mg 6-month formulation administered subcutaneously in the maintenance of PSA 	
 Percent change in PSA from baseline (prior to injection) at Day 169 and Day 337 (Percent change in PSA defined as the absolute value of difference between the PSA values at Day 169 and Day 337 and the baseline value divided by the baseline value)

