5.1 Inclusion Criteria

Participants are eligible to be included in the study only if all of the following criteria apply:

- (1) Participant is male and must be 18 years of age inclusive, at the time of signing the informed consent.
- (2) Participant has histologically or cytologically proven prostate cancer with rising PSA after failed local therapy or metastatic disease, or requiring radiotherapy, and be a candidate for long-term (i.e. >1 year) androgen deprivation therapy.
- (3) Participant requires a GnRH analogue treatment for a minimum of 18 months, of which a minimum of 3 months of GnRH analogue treatment has already been provided prior to screening. (Note: participants must receive study intervention on Day 1 in accordance with the treatment schedule of their previously received GnRH analogue therapy).
- (4) Has serum testosterone levels <1.735 nmol/L (50 ng/dL) at screening.
- (5) Has Eastern Cooperative Oncology Group (ECOG) performance status score of 0 to 1 (see Appendix 10.4).
- (6) Has a life expectancy of >18 months.
- (7) Male participants must agree that, if their partner is at risk of becoming pregnant (although highly unlikely in this study population), they will use an effective method of contraception. The participant must agree to use the contraception during the whole of the study and for 9 months after the last dose of study intervention.
- (8) Capable of giving signed informed consent as described in Appendix 10.1 which includes compliance with the requirements and restrictions listed in the informed consent form (ICF) and in this protocol.

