5.2 Exclusion Criteria

Participants are excluded from the study if any of the following criteria apply:

Medical conditions

- (1) Presence of another neoplastic lesion or brain metastases.
- (2) Metastatic hormone-sensitive prostate cancer with high tumour burden
- (3) Metastatic castration-resistant prostate cancer
- (4) Any concomitant disorder or resulting therapy that is likely to interfere with participant compliance or with the study in the opinion of the investigator.

Prior/concomitant therapy

- (5) Use of finasteride (Proscar®) or dutasteride (Avodart®/Avolve®) within the past 6 months
- (6) Planned intermittent scheme of GnRH analogue
- (7) At the time of screening, planned use of any chemotherapy for prostate cancer during the study
- (8) Prior hypophysectomy or adrenalectomy

Prior/concurrent clinical study experience

(9) Participation in another study with an experimental drug within 3 months before signing informed consent or within five half-lives of the investigational drug (whichever was the longer), or any other type of medical research.

Diagnostic assessments

(10) Severe kidney or liver failure (creatinine >2 times the normal range, aspartate aminotransferase and alanine aminotransferase >3 times the normal range)

Other exclusions

(11) Any concomitant disorder or resulting therapy that is likely to interfere with participant's compliance, the subcutaneous administration of the drug or with the study in the opinion of the investigator.

(12) Previous history of QT prolongation or concomitant use of medicinal products known to prolong the QT interval or with a known risk of torsades de pointes

(13) Known hypersensitivity to triptorelin or any of its excipients, GnRH, other GnRH agonist/analogue.

(14) Known active use of recreational drug or alcohol dependence in the opinion of the investigator

(15) Inability to give informed consent or to comply fully with the protocol.

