6.8 Concomitant Therapy

Any medication or vaccine (including over the counter prescription medicines, recreational drugs, vitamins, and/or herbal supplements) that the participant has taken within the last 2 months before or during triptorelin administration must be recorded on the eCRF along with:

- Generic or trade name
- Reason for use
- Dates of administration including start and end dates
- Dosage information including dose and frequency

The medical monitor should be contacted if there are any questions regarding concomitant or prior therapy.

The following concomitant medications are not permitted during the study:

- Finasteride or dutasteride
- Abiraterone
- Medications which are known to affect the metabolism and/or secretion of androgenic hormones: ketoconazole, aminoglutethimide, oestrogens.
- Systemic or inhaled corticosteroids (topical application permitted).
- Any herbal products previously used within 1 month prior to study start or plan to be used during the study, which are known to have cytotoxic effect or affect the metabolism and/or secretion of androgenic hormones.
- Medications known to prolong QT interval (class IA (e.g. quinidine, disopyramide) or class III (e.g. amiodarone, sotalol, dofetilide, ibutilide) antiarrhythmic medicinal products, methadone, moxifloxacin, antipsychotics).

The following concomitant medications are permitted during this study, but they must be monitored closely, and every effort should be made to keep their dose and dose regimen constant throughout the course of the study:

- Enzalutamide, apalutamide or darolutamide

- Analgesics: are allowed when necessary for pain relief.
- Anticonvulsants (e.g phenobarbital): long-term therapy may have additional risk for osteoporosis
- Other medications: any treatment which is considered necessary for the participant's welfare, may be given at the discretion of the investigator.

Other procedures: any diagnostic, therapeutic or surgical procedure performed during the study period should be recorded, including the date, indication, description of the procedure(s), and any clinical findings.

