7 DERIVED DATA

The following derived data will be calculated and included in the listings:

(1) Baseline value

Baseline value is defined as the last non-missing measurement taken prior to first IMP administration (including unscheduled assessments) (see section [5.1.3](#)).

(2) Duration of subject participation (study exposure)

Study exposure will be calculated as:

Study exposure (days) = last assessment or visit performed – informed consent date +1. It will be then divided by 30.4375 to be presented in months.

(3) Age

Subject age (years) will be as collected in eCRF.

(4) BMI

BMI (kg/m^2) will be derived as $\text{Weight} (\text{kg})/[\text{Height}(\text{cm})/100]^2$ and rounded to the nearest decimal.

(5) Time from diagnosis to screening

Time from diagnosis to screening will be calculated as (date of screening – date of diagnosis). It will be then divided by 30.4375 to be presented in months.

In case of missing screening day, the day will be imputed to 15. In case of missing screening month, the month will not be imputed.

In the same way, in case of missing diagnosis day, the day will be imputed to 15. In case of missing diagnosis month, the month will not be imputed.

No imputation will be performed for missing year.

(6) Compliance

Compliance will be calculated as:

Dose administered divided by dose planned to be administered multiplied by 100. The percentage of residual will be considered to determine the percentage of dose non-administered, and so the dose administered.

A total of two injections will be considered as planned dose administration in this study.

Associated Procedure / Instruction Reference	319480-SOP
Form Reference	080091-FOR v7.0

IPSEN GROUP

CONFIDENTIAL

D-FR-52014-245

SAP Final: Version 1.0: 30 January 2023

PAGE 27/43

(7) Percent change from baseline

Percent change from baseline will be calculated as:

$((\text{assessment at the visit} - \text{assessment at baseline}) / \text{assessment at baseline}) * 100$.

Zero will be used if both assessment at baseline and change from baseline are zero.

(8) Changes from baseline

Changes from baseline will be calculated as a difference from baseline (e.g. assessment at the visit – assessment at baseline).

(9) Study drug exposure

Study drug exposure will be calculated as:

Study drug exposure (days) = last study drug administration date – first study drug administration date +1. It will be then divided by 30.4375 to be presented in months.

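### PSA maintenance is credited to triptorelin, but the SAP has no PSA-specific rule for other prostate-cancer therapy started during the study

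*SAP*

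**What the plan says.** **Objective.** Protocol section 3 states: "To demonstrate the effect of triptorelin embonate 22.5 mg 6-month formulation administered subcutaneously in the maintenance of PSA". PSA is sampled on Day 1, Day 169 and Day 337 or early discontinuation (Protocol 1.3).

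**Definition.** SAP 5.7.3.1 makes the endpoint unsigned: "Percent change in PSA defined as the absolute value of difference between the PSA values at Day 169 and Day 337", relative to baseline. SAP section 7, item 7, under "Percent change from baseline will be calculated as", gives a signed formula: visit minus baseline, over baseline, times 100.

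**Analysis.** SAP 5.7.3.2 applies the primary-estimand strategies to the secondary endpoints in the FAS and then says: "For percent change in PSA from baseline at Day 169 and Day 337, descriptive statistics will be provided". No secondary subgroup analysis is planned (5.7.3.3). The only secondary sensitivity analysis concerns testosterone below 20 ng/dL (5.7.3.4).

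**Other therapy.** Protocol 6.8 lists "Enzalutamide, apalutamide or darolutamide" among permitted drugs. Sites are asked to try to hold dose and regimen steady, and any treatment needed for the participant's welfare is left to the investigator. Protocol 5.2 excludes "At the time of screening, planned use of any chemotherapy for prostate cancer during the study", and the list of disallowed drugs in 6.8 does not name chemotherapy. Protocol 5.1 admits men with "rising PSA after failed local therapy or metastatic disease, or requiring radiotherapy".

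**The concern.** The study has no control arm, so nothing in the data separates triptorelin from a therapy added later. The men most likely to receive added therapy are those whose PSA is rising. If it works, their later PSA values fall, and those values enter a summary that the objective attributes to triptorelin.

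Added therapy is foreseeable on the protocol's own account: "after 1 to 2 years of treatment, advanced prostate cancer eventually progresses to castration resistant prostate cancer" (Protocol 2.2). Entry requires at least 3 months of earlier GnRH analogue treatment, and Day 337 adds about 11 months (337/30.4375 = 11.1). A man who reaches Day 337 has therefore had about 14 months or more, which lies within or beyond that period.

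At stake is whether the report can say that PSA was maintained on triptorelin. The castration result is not at stake.

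**Working it through.** **1. Does such a man stay in the analysis?** The FAS (SAP section 4) depends on two injections and the testosterone visits. The only efficacy-based withdrawal rule in Protocol 7.2 is defined by testosterone. A man who stays castrate, has a rising PSA, starts a permitted drug and attends all visits is in the FAS with his later PSA values.

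**2. Does a rule deal with those values?** The strategies in SAP 5.7.2.1, set beside the PSA endpoint:

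| Rule | What it covers | Effect on PSA after a new therapy |
|---|---|---|
| ICE 1 to 3 | Study discontinuation, missing testosterone, no second injection | None for a man who completes |
| ICE 4 | Prohibited drugs judged to affect testosterone; counted as non-responder | Does not reach permitted drugs; non-responder has no meaning for a continuous percent change |
| Treatment regimen | Triptorelin plus possible permitted concomitant drugs | Values kept, by implication |

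So the values are retained, without a rule written for PSA. (The regimen text points to Protocol 6.3 for the permitted drugs; the list is in 6.8.)

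**3. The plan's own figures.** The only design figures are for castration. With n = 130, null rate 0.90 and assumed rate 0.97, the exact test needs at least 124 men maintained. Its one-sided alpha is 0.0207 and its power 0.9027. Enrolment is 130/0.9 = 144.4, hence 145. These reproduce, and none bears on PSA.

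**4. One man.** Assumed values: baseline 2, rise to 6 between samples, then new therapy. That such therapy lowers PSA is also my assumption; the documents do not state it.

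| PSA at visit | Signed change | Absolute change |
|---|---|---|
| 6 (no therapy) | +200% | 200% |
| 2.4 | +20% | 20% |
| 2 | 0% | 0% |
| 0.2 | -90% | 90% |

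A return towards baseline reads as little change on both definitions. A deep fall reads as a decrease on the signed formula and as a large change on the absolute one.

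**5. Group mean.** Assume a share f of 130 men start therapy, would otherwise be at +100%, and are observed at -80%.

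- Signed shift = f × (100 - (-80)) = 180f
- Absolute shift = f × (100 - 80) = 20f
- If PSA instead returns to baseline, both definitions shift by f × (100 - 0) = 100f

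| f | Men of 130 | Signed, -80% | Absolute, -80% | Either, back to baseline |
|---|---|---|---|---|
| 5% | 6.5 | 9 points | 1 point | 5 points |
| 10% | 13 | 18 points | 2 points | 10 points |
| 20% | 26 | 36 points | 4 points | 20 points |

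If all other men are at 0%, the median is 0% with or without the therapy, because at least 80% of men sit there.

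**6. Would the untreated men alone give the answer?** With f = 10% and the other men at 0%, the mean had nobody been treated is 0.10 × 100 = +10%. Dropping the starters gives 0%. The failures vanish again, so that subgroup cannot carry the maintenance statement.

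**The case against.** A reader might infer that no rule at all covers added therapy. The documents do not support that. SAP 5.7.3.2 imports the primary strategies, and the regimen in 5.7.2.1 includes permitted drugs. Keeping PSA values after such a drug can be read as an estimand choice. This stands, and it narrows the point: the rule was built for testosterone, and it yields an estimate for triptorelin plus permitted therapy while the objective names triptorelin alone.

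A reader might also infer that every treated rise would read as maintained PSA, or that the reported mean moves by 18 points. Neither follows. The plan sets no threshold for maintained, a deep fall counts as a large change on the endpoint's definition, and the 18 points hold only for signed change under assumed inputs. Medians and quartiles are also planned (SAP 5.1.2).

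Other limits are fair. Asking sites to hold permitted drugs steady suggests stable background use, though it does not bar a new start. Excluding metastatic castration-resistant and high-burden metastatic hormone-sensitive disease, and requiring life expectancy above 18 months, should lower the rate of added therapy. The planned listings flag treatments that begin on or after first dose (SAP 5.5), so an analyst could trace these men by hand; no planned output links them to PSA.

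Finally, a single-arm study cannot isolate triptorelin's PSA effect whatever this table shows. That is true, and it is a reason to label the summary for what it estimates.

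**Conclusion.** The point holds in a limited form. Prostate-cancer therapy may be started on study, the PSA values after it stay in the FAS summary, and no PSA-specific intercurrent-event rule or PSA sensitivity analysis exists. A rise treated back towards baseline would be summarised as little change and attributed to triptorelin.

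The actual size is unknown, because the documents give neither a rate of new therapy nor expected PSA values. On the assumptions above, a 10% start rate moves the mean by 18 points signed, 2 points absolute, or 10 points on either definition if PSA returns to baseline. The median would hardly move. That the size depends so heavily on the definition is itself a reason to reconcile SAP 5.7.3.1 with SAP section 7.

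The endpoint is secondary, descriptive and untested. The castration conclusion is unaffected, and nothing here supports a wider doubt about the trial. This is an inexpensive improvement worth making.

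**What to change.** In the SAP:

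1. Keep the all-participant PSA summary and label it as triptorelin plus permitted therapy.
2. Name the start or change of prostate-cancer therapy (drug, radiotherapy or surgery) on or after Day 1 as an intercurrent event for PSA. Report how many men had it before the Day 169 sample and how many before the Day 337 sample.
3. At each visit, show signed PSA change separately for men with and without such therapy begun or changed before that visit. Classifying by visit keeps a man who starts after Day 169 in the unaffected group for his Day 169 value.
4. Do not rest the maintenance statement on the untreated group alone, since it is selected after baseline. Count new starters as men in whom maintenance on triptorelin alone was not shown.
5. Reconcile the absolute and signed definitions of percent change.

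The cost is SAP wording and one extra descriptive table. Protocol 6.8 already collects drug dates and dosage and the dates of procedures, and SAP 5.5 already classifies drugs, non-drug therapies and surgical procedures by start date. Study conduct does not change. The downside is that the two groups are formed after baseline and the treated group may be small, so the table describes and does not estimate a treatment effect.
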